Participant contact: The research team will utilize both email and Avocado (a messaging platform that facilitates text message communication between research staff and study participants without staff member using their personal phone numbers for the study; already vetted by the OIT) when communicating with participants in the study. Access to Avocado inbox used for this study will be limited to necessary study staff. Participants will be asked to indicate their preferred method of contact on the contact form (after consent) and will be contacted only via their selected method.

Baseline (T1), post-intervention (T2), and 3-month follow-up assessments (T3): At each timepoint, participants will complete a Qualtrics survey, which will be accessed through a unique link created based on each participant's deidentified participant identification number (PID).

The Baseline assessment (T1) will include a set of sociodemographic questions as well as a total of 27 scales, measuring depression, anxiety, PTSD, functional impairment due to depression, functional impairment due to anxiety, interoceptive awareness, de-centering, rumination/perseverative thinking, theories of psychological distress, theories of emotion, internalized stigma, emotion regulation, loneliness, mindfulness, self-compassion, perceived stress, political stress, sleep, phone use, early life adversity, childhood trauma, experiences of stress and adversity, everyday experiences of discrimination, rejection sensitivity, Major Depressive Episode, Generalized Anxiety Disorder, and overall well-being (see "Compiled Measures_GEM.docx").

Additionally during the Zoom call for baseline assessment (T1), the RA will "onboard" the participant and (a) review how to use a FitBit, (b) install the study application, and (c) problem solve any logistic issues. The baseline assessment and onboarding will take a total of 90-120 minutes.

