The post-intervention assessment (T2) will take place 1-2 weeks after the recommended modules are completed and include a total of 26 scales, measuring depression, anxiety, PTSD, functional impairment due to depression, functional impairment due to anxiety, interoceptive awareness, Major Depressive Episode, Generalized Anxiety Disorder, de-centering, rumination/perseverative thinking, theories of psychological distress, theories of emotion, internalized stigma, emotion regulation, loneliness, mindfulness, self-compassion, perceived stress, political stress, sleep, phone use, applied mindfulness process, overall well-being, client satisfaction, session evaluation, and adverse effects. The post-intervention assessment will take a total of 60-90 minutes.

Additionally at T2, participants will be invited to complete an exit interview via Zoom, the University approved web conferencing platform. Interview will take 90-120 minutes. In line with previous studies from our team, the interview will be recorded using the native recording feature on the Zoom platform (i.e., capturing both video and audio recording) and saved to the interviewer's Brown Zoom cloud. The RA recording the interview will ensure that the setting "Allow cloud recording sharing" is disabled on

Zoom. By disabling this setting, nobody other than the person who made the recording will be able to access that recording on the cloud. Therefore the recording saved to the interviewer's Brown Zoom cloud will be only accessible to the interviewer creating the recording. An audio-only recording file will be downloaded from the Zoom cloud to Stronghold, and the original recording will be deleted from the Brown Zoom cloud.

At follow-up assessment (T3), which will take place 3 months after the baseline assessment, we will include a total of 21 scales, measuring depression, anxiety, PTSD, functional impairment due to depression, functional impairment due to anxiety, Major Depressive Episode, Generalized Anxiety Disorder, interoceptive awareness, de-centering, rumination/perseverative thinking, theories of psychological distress, theories of emotion, internalized stigma, emotion regulation, loneliness, mindfulness, self-compassion, perceived stress, political stress, sleep, phone use, applied mindfulness process, and overall well-being. The follow-up assessment will take a total of 60-90 minutes.

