At each of these assessments, participants will join a Zoom meeting with an RA. To mitigate confidentiality risks and risk of third-party participants, The RA will begin the call by instructing participants to complete the procedure in a private location. Participants will be reminded to pause the assessment if another person enters the space. Then, the RA will verbally administer MINI-Major Depressive Episode and MINI-Generalized Anxiety Disorder. Before beginning the MINI modules, RA will remind participants that if they disclose information indicating imminent risk of serious harm to themselves or others, this information must be reported to relevant law enforcement or other authorities. During the assessment, the RAs will have access to a Qualtrics survey with both measures, which will serve as their guide to administer the measures (refer to "Compiled Measures_GEM.docx" for the scale and questions asked). The Qualtrics survey will be accessed only by the RA (i.e., the survey won't be sent directly to the participant) and filled out by the RA as the assessment progresses. The Qualtrics data will only be linked to the participant ID number (deidentified only) and will be kept in a secure location with other de-identified data. After both MINI modules are administered, the participant will be given access the aforementioned unique Qualtrics link to complete the rest of the measures, during which time the participants can ask any questions as they come up during the assessment.

For participants who report suicidality in the MINI-Standard: Major Depressive Episode module, the suicide safety assessment and plan will be followed accordingly (refer to document named "Suicide Safety Plan_GEM.docx and to Section 18.0). Because all eligible participants at this point will have only mild to moderately severe symptoms of depression (individuals with severe symptoms are screened ineligible at the Qualtrics screener survey), there is low likelihood that a participant will be at imminent risk of suicide; however, the suicide safety assessment and plan has been developed out of an abundance of caution. The Suicide Safety Assessment and Plan will be conducted by [name], a licensed psychologist and the principal investigator of the study, or by a study team member who has been formally trained by [name] and

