In addition to the weekly modules, participants will take part in a weekly, 1-hour "Group practice and connect" session on Zoom. The online sessions will comprise a cohort of 5-10 participants (depending on recruitment) and will be led by a research assistant, who has previous experiences with mindfulness programs as well as lived experiences of early life adversity. During each session, participants will be invited to participate in a group practice and reflection and to join group discussions on experiences regarding past week's practice. In the contact form (which is completed after the consent form), participants will be presented with the day and time of weekly sessions for the next two cohorts and asked to choose the times they are available for. If the participant is not available for either of the offered times, they will be marked as "deferred enrollment" in our participant tracking spreadsheet. A study RA will follow up with information about future cohort scheduling as that information becomes available.

Ecological momentary assessments and interventions: Over the first 4 weeks of the intervention period (i.e., Recommended Modules), participants will also complete 3 EMAs + EMIs per day through Expiwell. EMA and EMI will be delivered concurrently; the EMA will collect participant's response on their current mood, recent stressful experience, and type of stressor; participants will then receive a list of mindfulness exercises, which will be tailored to the type of stressor/emotion they will have indicated. The last EMA of the day will also include an option for the participants to submit a voice recording, serving as a "daily journal" at the end of the day to understand participant's daily experiences, including daily stressors and mindfulness practice application. To mitigate the risk of recording third-party participant voices, participants in the study will be

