Analytic Plan

V1_3.9.2026

Indicator	Benchmark Target
Recruitment	> 60% of eligible and approached participants enroll in the study.
Retention	> 70% retention of enrolled participants (complete final T2 post-intervention assessments).
Intervention Acceptability	> 75% of participants report a score of 24 or more on the Client Satisfaction Questionnaire (CSQ-8), indicating "good" satisfaction.
EMA Adherence	> 50% of participants complete 50% of the daily EMA prompts.
Audio Module Adherence	> 60% of participants complete 50% of the weekly audio modules for 4 weeks.

We will apply predefined benchmarks (see above) to assess the primary outcomes of feasibility and acceptability. Scores from the CSQ-8 and Session Evaluation Form (SEF) will be calculated and summarized using descriptive statistics (means, standard deviations, frequencies). Adherence will be calculated objectively via system-captured app data: EMA compliance will be calculated as the proportion of completed prompts out of total expected prompts, and audio compliance as the proportion of modules played to completion. Engagement outcomes will summarize completion of audio modules, use of meditation recordings/practices, and engagement in EMI.

Qualitative Exit Interviews To contextualize the quantitative acceptability data, semi-structured exit interviews will be conducted at T2 to explore: (a) perceived relevance, usability, and content preference of the audio modules, along with weekly peer sessions; (b) participant experience with the burden and frequency of the daily EMA prompts (3–4 per day) and the weekly audio volume (5–10 per week); (c) feedback on the module delivery (e.g., preference for batch release vs. daily drip); (d) perceived impact of the GEM intervention on daily target behaviors (mood) and depression/anxiety prevention; and (e) suggestions for content adaptation, pacing, and refinement to reduce participant burden in future efficacy trials.

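### At T2 the CSQ-8 is completed with a study RA reachable on Zoom, possibly the participant's own group leader, which risks upward courtesy bias in the acceptability benchmark

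*Protocol*

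**What the plan says.** **Setting.** Protocol 6.2, on the conduct of T1 to T3: "At each of these assessments, participants will join a Zoom meeting with an RA". The RA first administers two MINI modules aloud and enters the answers in a survey that only the RA opens. For everything else the participant is then given a "unique Qualtrics link to complete the rest of the measures, during which time the participants can ask any questions". That link is built on the "deidentified participant identification number (PID").

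**Content.** The T2 scale list in Protocol 6.2 ends with "client satisfaction, session evaluation, and adverse effects". The conduct paragraph exempts none of these three.

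**Staff roles.** The weekly group "will be led by a research assistant, who has previous experiences with mindfulness programs as well as lived experiences of early life adversity" (Protocol 6.2; 5.2 says the same). Protocol 6.4 has the exit interview done on Zoom with an RA. Neither document says whether these must be different people.

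**Use of the result.** The SAP states: "We will apply predefined benchmarks (see above) to assess the primary outcomes of feasibility and acceptability". Its acceptability row requires "> 75% of participants report a score of 24 or more on the Client Satisfaction Questionnaire (CSQ-8"). The SEF is summarised descriptively and has no target.

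**The concern.** The CSQ-8 asks participants to judge the programme. They give that judgement during a call with a member of the team that delivers it. This may be the person who led their group of 5 to 10 through four weekly one-hour sessions and who shares the experience of early adversity. Reluctance to criticise is plausible in that setting, and its expected direction is towards higher scores.

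Three features of the plan make this matter.

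- The CSQ-8 share is the only satisfaction benchmark among the primary outcomes, and it is read as pass or fail.
- The trial has one arm, so no comparator shares the setting and absorbs the effect.
- The SAP uses the exit interviews to put the satisfaction scores in context. If the interviewer led the group, that check has the same weakness.

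Bias that enters when the form is completed cannot be removed in the analysis, so any change has to be made before T2 assessments begin.

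**Working it through.** **Step 1. What the text establishes.**

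| Question | Protocol text | Status |
|---|---|---|
| Are the CSQ-8 and SEF part of T2? | 6.2, T2 scale list | Stated |
| Is an RA reachable while they are completed? | 6.2: Zoom meeting, questions allowed during completion | Natural reading |
| Does the RA see the answers? | 6.2: only the MINI survey is RA-completed | Not stated |
| Is the T2 RA or exit interviewer the participant's group leader? | 5.2, 6.2, 6.4: each is an RA | Left open |
| Are the roles separated, or does the call end before the ratings? | No provision found | Absent |

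**Step 2. The plan's own figure.** Protocol 12.2 aims for at least 35 of 44 participants completing, about 80%. 35/44 = 79.5% and 0.80 × 44 = 35.2, so the figure reproduces. The documents give no error rate or precision for the CSQ-8 benchmark.

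**Step 3. Passing counts.** The target is strictly more than 75%, so the smallest passing count is floor(0.75n) + 1.

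- n = 35: 0.75 × 35 = 26.25, so 27 are needed.
- n = 31: 0.70 × 44 = 30.8, so 31 is the fewest T2 completers that meet the retention benchmark. 0.75 × 31 = 23.25, so 24 are needed.
- n = 44 (no loss): 0.75 × 44 = 33, so 34 are needed.

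This takes the denominator to be participants who complete the CSQ-8, which is an assumption.

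**Step 4. Chance of passing.** With X ~ Binomial(n, p), where p is the observed-response rate, P(pass) = P(X ≥ passing count):

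| n (needed) | p = 0.60 | 0.65 | 0.70 | 0.75 | 0.80 | 0.85 |
|---|---|---|---|---|---|---|
| 31 (24) | 0.033 | 0.101 | 0.245 | 0.473 | 0.730 | 0.918 |
| 35 (27) | 0.026 | 0.089 | 0.234 | 0.474 | 0.745 | 0.931 |
| 44 (34) | 0.012 | 0.057 | 0.189 | 0.442 | 0.746 | 0.943 |

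**Step 5. Reading it as a shift.** Suppose the true rate is 70% and n = 35. An assumed shift of 5 points moves the pass probability from 0.23 to 0.47, and 10 points moves it to 0.75. From a true rate of 65%, the same shifts move it from 0.09 to 0.23 and 0.47. In counts, 25/35 (71.4%) and 26/35 (74.3%) fail, while 27/35 (77.1%) passes. Near the threshold, one or two changed answers settle the result.

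**The case against.** The strongest reply is that no bias has been demonstrated. The CSQ-8 is self-completed on a coded link, participants are asked to be somewhere private, and nothing says that the RA sees the screen or the answers. The group leader is described by specific experience, while the assessor is simply an RA. The measures and interview guides that the protocol cites were not available and may contain further instructions. The 70% starting rate and the shifts are assumed, and any cut-off at this sample size would move in the same way under a shift from any cause. At a true rate of 85% the benchmark already passes with probability 0.93. The EMA and audio adherence benchmarks come from app data, which courtesy on a call cannot affect.

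Most of this stands, and it rules out several readings that a reader might infer:

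- *The benchmark is biased upward.* The documents support a risk in that direction, not a fact or a size.
- *Participants rate the programme under observation.* They rate it with an RA reachable, which is weaker.
- *The assessor is the group leader.* The text allows this but does not state it.
- *The SEF helps decide the verdict.* It has no threshold.
- *Harms would go unseen.* EMA responses are monitored daily, and PHQ-9 and GAD-7 are collected weekly during the first four weeks, so the T2 form is not the only source.

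What the reply does not remove is the setting itself. A coded link can still be traced to the participant by the study. The instruction in Protocol 19.2 to use neutral, supportive language does not settle who is present. The adherence benchmarks measure use, not satisfaction.

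**Conclusion.** The concern holds as a risk. The one satisfaction benchmark among the primary outcomes is collected with a study RA reachable on the call, no rule keeps that RA or the exit interviewer distinct from the participant's group leader, and the trial has no comparator.

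The size of any bias is unknown. The sensitivity figures show only that the verdict is fragile if the true rate lies near 75%. They rest on assumed true rates, assumed shifts, independent responses and a denominator of CSQ-8 completers. If the true rate is well away from the threshold, a modest shift matters much less. The point merits a change because the remedy is small and has to be in place before data collection, not because the result is known to be distorted.

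**What to change.** In Protocol 6.2:

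1. Put the CSQ-8 and SEF in a final T2 Qualtrics block, on the same coded link, completed after the Zoom call ends. If that is impractical, state that the RA is off camera and does not view responses.
2. Keep the adverse-effects scale where it is. Moving it off the call would remove live staff contact when harm is reported.
3. Restrict group leaders' access to individual CSQ-8 and SEF answers, and tell participants so. Protocol 17.2 and 19.3 currently give research personnel broad access, so the assurance is true only if the restriction is actually made.
4. Where existing staffing allows, have T2 calls and exit interviews run by an RA who did not lead that cohort. Otherwise, record the overlap and report it as a limitation beside the benchmark result.

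The cost is survey-flow and scheduling wording plus an access setting. No scale, visit or sample-size change is needed. The number of RAs is not given, so item 4 may not be possible for every cohort. The downside is some extra missing CSQ-8 and SEF data, because Protocol 19.2 lets participants skip questions. This is limited because Protocol 13.5 makes T2 payment depend on survey completion. Because the SAP defines retention by T2 completion, it should also say whether an unfinished final block counts as complete.

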2.0 Objectives

- 2.1 The objectives of this study are to: (a) examine the feasibility, acceptability, and preliminary efficacy of a mindfulness-based, app-delivered intervention to address mental health and emotion regulation challenges experienced by young adults with early life adversities (ELAs); and (b) understand mechanisms of change underlying the intervention, including the role of mindfulness (i.e., interoceptive awareness and de-centering), rumination, and sleep using real-time data collection via ecological momentary assessments (EMAs) and wearable devices.
- 2.2 We hypothesize that young adults will find the Growth, Empowerment, and Mindfulness (GEM) intervention to be both feasible and acceptable, as demonstrated by participants' engagement and quantitative/qualitative feedback; we also hypothesize that the engagement with the intervention will demonstrate preliminary efficacy for improving outcome measures including depression, anxiety, self-compassion, emotion regulation, loneliness, and healthier phone use. We further hypothesize that the mechanisms underlying the benefits of the intervention will be improvements in mindfulness and sleep, as well as reductions in rumination.

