In addition to the weekly modules, participants will complete EMAs and EMIs 3 times per day during the Recommended Modules (i.e., first four weeks of intervention period). The EMI will be delivered concurrently with the EMA, which will collect participant’s response on their current mood, recent stressful experience, and type of stressor. Participants will then receive a list of mindfulness exercises, which will be tailored to the type of stressor/emotion they will have indicated. The intervention as well as EMAs and EMIs will be delivered on a mobile application named “Expiwell” (<https://www.expiwell.com/>).

At the end of each week, participants will also take part in a weekly “Group practice and connect” session on Zoom during the Recommended Modules (i.e., first four weeks of intervention period). The weekly sessions will be conducted in cohorts of 5-10 participants (depending on the recruitment speed), led by a research assistant who has previous experiences with mindfulness programs as well as lived experiences of early life adversity. Each session will last approximately one hour and will be structured roughly to reflect: group check-in, group discussion on past

week's weekly intervention content, one group meditation practice using audio, and reflections on the meditation practice.

- 5.3 This study will utilize Fitbit, a commercially available wearable device, for the purpose of passive data collection on sleep and physical activity. The Fitbit devices will be stored securely by the research team when not in use, distributed directly to participants during enrollment by mail, and collected at the end of the study. Names and addresses of participants will be shared with departmental operations staff through password-protected files to create shipping labels and facilitate mailing the Fitbits to participants via FedEx. When operations staff submit reconciliation for the transaction, it is on an aggregate level (i.e., without specific participant information or individual package tracking numbers). This ensures the confidentiality of each participant. Participants will be instructed on proper use and care of the device, and a pre-paid, pre-addressed return envelope will be provided so participants can directly mail the device back to the research team at the end of the study. Only authorized study team members will manage device distribution, collection, and data linkage.

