instructed to complete the voice recording in a private location and to ensure no other individuals are present or speaking during the recording. Participants will be reminded to pause, stop, or restart the recording if another person enters the space. Participants will also be reminded that the voice recording is optional--they may skip voice recording submission without penalty and still receive compensation. Audio will be downloaded from Expiwell, uploaded to Stronghold, then deleted from Expiwell's storage. The audio housed in Stronghold will be deleted after they are transcribed and vetted for accuracy by study staff. A research assistant will monitor responses to the EMA on a daily basis (including the voice recording, where a transcript will automatically become available through Expiwell's AWS service). Any reportable events that are observed will be reported to the PI, and the PI will be available to meet, if necessary, to review concerns regarding a particular participant or any problems that may arise for participants.

Weekly assessments: During first 4 weeks of intervention period (i.e., Recommended Modules), participants will be asked to complete a survey every week. The survey consists of 2 scales (PHQ-9 and GAD-7) as well as 3 items from interoceptive awareness scale, 3 items from de-centering scale, 3 items from perseverative thinking scale, and 1 item from theory of distress scale. Each survey will take 4-5 minutes, with a total of 16-20 minutes over the 4 week period.

Wearable device: Also during the first 4 weeks of intervention period (i.e., Recommended Modules), data will be collected from a Fitbit from each participant. Data collected include total sleep time, sleep onset latency, REM and non-REM sleep duration, sleep/wake variability, and resting heart rate. Each participant will be mailed a Fitbit from the study team along with a pre-paid return envelope at the enrollment in the study. These devices will be assigned to participants and linked to de-identified study accounts only. Participants will be instructed to wear the Fitbit device daily, before going to bed, for the entire 4-week period. At the end of the intervention, participants will be asked to return the Fitbit using the pre-paid return envelope.

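### The Fitbit records no nights before the intervention, so change in device-measured sleep from before GEM cannot be estimated directly

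*Protocol*

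**What the plan says.** **Aim.** Protocol 2.1(b) sets out to study sleep as a mechanism using real-time data from EMA and wearables. Section 2.2 hypothesises that "the mechanisms underlying the benefits of the intervention will be improvements in mindfulness and sleep, as well as reductions in rumination".

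**Collection window.** Section 6.2, under the wearable device: "Also during the first 4 weeks of intervention period (i.e., Recommended Modules), data will be collected from a Fitbit from each participant". The wear instruction matches: "Participants will be instructed to wear the Fitbit device daily, before going to bed, for the entire 4-week period".

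**Device logistics.** Section 6.2 says: "Each participant will be mailed a Fitbit from the study team along with a pre-paid return envelope at the enrollment in the study". Section 5.3 agrees that devices are "distributed directly to participants during enrollment by mail". At the T1 call the research assistant will "review how to use a FitBit". On return, Section 6.2 says: "At the end of the intervention, participants will be asked to return the Fitbit using the pre-paid return envelope". Section 5.3 instead places the return at the end of the study. The two should be reconciled, but neither adds nights before Week 1.

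**Other sleep data.** A self-report sleep scale is given at T1, T2 and T3. The EMA content described in 6.2 and 6.4 covers mood, stress and emotional state, and the weekly survey contains no sleep scale.

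**Analysis.** The data analysis paragraph of 6.2 bases preliminary effects on the T1-T3 surveys and EMA. Section 17.1 lists sleep quality among outcomes for mixed models with time as a fixed effect, without saying which sleep measure. The SAP describes no analysis of Fitbit data.

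**The concern.** An improvement is a change from an earlier state. For the device measures (sleep duration, time to fall asleep, sleep stages, variability, resting heart rate) the plan records no earlier state. Every planned night falls after the participant has begun modules, EMI prompts and group sessions. With a single arm, no concurrent group can stand in for the missing reference.

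The other proposed mechanisms (interoceptive awareness, de-centering, rumination) are each measured at T1 and T2. On the content described, the Fitbit is the only real-time source on sleep and the only objective one. At stake is whether the pilot can give a before-to-during effect size for device-measured sleep to inform a later trial. Once a participant starts Week 1, those nights cannot be recovered.

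**Working it through.** The documents give no effect size, standard deviation or power for sleep, so there is no planned figure to reproduce. The check has two parts.

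**1. Count the nights (Protocol 6.2).**
- Before Week 1: 0 requested.
- Weeks 1-4: 4 × 7 = 28.
- After Week 4: 0 requested.

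**2. Ask what the 28 nights can recover.** The trajectories below are assumptions, because the documents give none. Let D be the true change from before the intervention to the end of Week 4, and m1 to m4 the four weekly means, measured from the pre-intervention level. Three summaries are compared; none is specified for Fitbit data in the documents.
- Week contrast: m4 − m1.
- Slope over four weeks: the least-squares weekly slope is [3(m4 − m1) + (m3 − m2)]/10, multiplied by 4. This is one way to read the time effect in Section 17.1.
- Change from a run-in baseline: m4 − 0.

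| Assumed trajectory | m1, m2, m3, m4 | Week contrast | Slope × 4 | From run-in |
|---|---|---|---|---|
| Linear over 4 weeks | D/8, 3D/8, 5D/8, 7D/8 | 0.75D | 1.00D | 0.875D |
| Linear to a plateau at end of Week 1 | D/2, D, D, D | 0.50D | 0.60D | 1.00D |
| Immediate shift | D, D, D, D | 0 | 0 | 1.00D |
| Worse by E in Week 1, then back to the starting level (D = 0) | −E, 0, 0, 0 | +E | +1.2E | 0 |

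The slope entries are:
- Linear: [3(0.75D) + 0.25D]/10 = 0.25D per week; × 4 = D.
- Plateau: [3(0.5D) + 0]/10 = 0.15D per week; × 4 = 0.60D.
- Immediate: 0.
- Early worsening: [3E + 0]/10 = 0.3E per week; × 4 = 1.2E.

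A steady change therefore needs no run-in if a slope is fitted. A front-loaded change is partly or wholly missed. Early worsening followed by recovery would look like improvement where there was none. That case is not fanciful: Section 15.1 lists insomnia among reported effects of meditation.

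**The case against.** A reader might infer that the sleep hypothesis has no baseline at all. The documents do not support that. Section 2.2 speaks of sleep, not of objectively measured sleep, and the self-report scale is given before and after the intervention.

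A reader might also infer that the wearable part of the objective cannot be answered. That too goes too far. Fitbit nights share a window with the EMA prompts and the weekly PHQ-9 and GAD-7, so trends within the intervention and associations between a night's sleep and the next day's mood or engagement remain open. The documents' real-time analyses are of this within-person kind, although none names Fitbit data.

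Third, a reader might infer a fixed loss, or a bias always toward no change. Neither follows. No passage plans to subtract Week 1 from Week 4, a slope recovers a linear change in full, and the sign depends on the trajectory.

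Two further points stand. The primary outcomes are feasibility and acceptability benchmarks, none of which uses the Fitbit. And even with a baseline, a before-after change in one arm could not be attributed to GEM. These limit the weight of the point. They do not supply the missing reference nights. Nor would run-in nights alone cure the absence of a Fitbit analysis from the SAP.

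**Conclusion.** The point holds in limited form. With 0 nights before and 28 during the intervention, change in Fitbit sleep and resting heart rate from before GEM cannot be estimated directly, and a shift early in Week 1 is largely missed. Under the assumed shapes, the slope recovers anything from none of the change (immediate shift) to all of it (linear), and it can show spurious improvement if sleep worsens first. No single figure for the loss is justified.

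The conclusion rests on the collection window and wear instruction in 6.2 and on finding no request for earlier wear elsewhere in the documents. That the device would arrive before Week 1 is an inference from mailing at enrolment and review at T1; the documents give no interval between T1 and Week 1. This is a worthwhile, inexpensive improvement to a secondary objective and leaves the primary outcomes untouched.

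**What to change.** In Protocol 6.2:
- Instruct participants to wear the Fitbit from the T1 onboarding call.
- Schedule T1 about 7 nights before the cohort's Week 1 where feasible. Make this a target, not a condition for unlocking content, so that late-onboarded participants are not pushed out of their cohort.
- Define the Fitbit baseline as the mean of the available nights before Week 1.

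In the SAP, add a Fitbit analysis that expresses Weeks 1-4 as change from that baseline.

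**Cost.** About one extra week of wear and of device time per participant, and tighter scheduling around cohorts of 5-10 with set session times. T3 falls 3 months after baseline, so an earlier T1 shortens follow-up after the intervention by up to a week unless T3 is re-anchored. It also moves the T1 survey values further from the start of the intervention. No extra visit is needed.

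**If run-in nights cannot be obtained**, state in the Protocol and SAP that Fitbit sleep is analysed only within the intervention, and that pre-post change in sleep rests on the self-report scale. This costs only wording.
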